## II – CONTEXT AND JUSTIFICATION OF THE RESEARCH: RATIONALE PRESENTING THE CONTEXT AND THE RESEARCH HYPOTHESES

Intravitreal injections (IVT) of anti-vascular endothelial growth factor (VEGF) and corticosteroids are the standard treatment to combat various retinal pathologies such as neovascular age-related macular degeneration (AMD), macular edema occurring during retinal vein occlusions, diabetic macular edema, high myopic neovascularization, ... [1]

An injection of these anti-factors stops the proliferation of abnormal vessels and reduces macular edema [2].

These injections are very effective but must be renewed regularly (on average every 2 months), for several years. Despite the anesthesia (usually topical) administered before each injection, some patients complain of feeling discomfort or even pain when placing the blepharostat (the device that keeps the eyelids apart) and inserting the needle through the sclera. [3]

Although the percentage of patients perceiving severe pain during an IVT session is low [4], pain management for these patients represents an important issue not only for their comfort but also for treatment compliance. It is important to reduce it effectively to improve patient management. The patient requires pain management when the score is greater than 3-4/10 on the VAS (Visual Analogue Scale which is the reference scale) [5].

Topical anesthesia using anesthetic drops (Tetracaine® or Oxybuprocaine®) is the reference method.

It is also possible to offer patients topical anesthesia by the instillation of eye drops (Tetracaïne® or Oxybuprocaina®) associated with so-called "improved" topical anesthesia  
» by the preoperative instillation of a drop of lidocaine gel: Ophtesic®. This protocol has obtained the favorable opinion of the ANSM but is currently little used. [6]. Several studies have proven the safety and efficacy of lidocaine gel for anesthesia during eye surgery [6–9]

In our practice at the IOO, we use the reference method as first intention, and we offer lidocaine gel to people complaining of having had pain during previous IVT sessions.

This practice carried out at the IOO has never been evaluated. In addition, there are several studies dealing with pain at the time of injection [10–17] and comparing different anesthetics [18–20], however they were carried out on a non-targeted population.

According to the HAS report[21]: "OPHTESIC 20 mg/g (lidocaine), ophthalmic gel in a single-dose container, does not provide any improvement in actual benefit (ASMR V) compared with anesthetic eye drops in the topical anesthesia during ophthalmic procedures. ". However, in our practice, patients who received topical anesthesia for IVT using anesthetic drops (Tetracaine® or Oxybuprocaine®), associated with a drop of lidocaine gel, report less pain, especially when placing the blepharostat.

The aim of this study, which includes two parts, is to better understand the prevalence of pain and its intensity during IVT and then to evaluate the effectiveness of the protocol using a drop of lidocaine gel on a targeted population (patients with a VAS score  $\geq 4/10$ ) in order to improve the management of patients complaining of severe pain during the injection.

We will first assess the perception of pain and its intensity during IVT using questionnaire 1. Once this step has been completed, we will suggest that the patients who have felt the most pain (VAS  $\geq 4/10$ ) and who have chosen to switch to anesthesia with lidocaine gel will again assess the pain felt with questionnaire 2.

The study will therefore consist of analyzing the responses to a survey carried out using 2 questionnaires offered during 2 IVT sessions for the same patient:

- **Quiz 1:** survey carried out in the context of anesthesia with the reference method
- **Quiz 2:** survey carried out during improved anesthesia (protocol to be evaluated): Tetracaine® or Oxybuprocaine® eye drops combined with a drop of lidocaine gel.

Pain being strongly correlated with the psychological state of the patient, and his degree of anxiety before the injection [13] , a psychological evaluation of the patient before the intervention will be carried out using the HAD Anxiety Scale (Hospital Anxiety and Depression Scale) by AS Zigmond and RP Snaith (French Translation JL Lépine) during the 2 questionnaires.

### III – OBJECTIVES AND JUDGMENT CRITERIA

MAIN OBJECTIVE	The main objective of this study is to evaluate the relief provided by so-called "improved" topical anesthesia by the preoperative instillation of a drop of lidocaine gel in addition to a drop of the anesthetic Tetracaine® or Oxybuprocaine® in patients perceiving severe pain during IVT compared to the reference anesthesia protocol.
MAIN JUDGMENT CRITERIA	
EVA Score: The figure will be rounded to the nearest millimeter
 
Comparison of the pain score felt during the injection during the 1st evaluation (with conventional anesthesia) with the pain score obtained during improved anesthesia.

SECONDARY OBJECTIVES	
 
1- Confirmation of pain relief with the score obtained on the simple verbal scale
 
2- Description of the prevalence and intensity of pain experienced by patients during IVT
 
3- Description of the psychological state of the patient during a IVT and validation of score stability
 

	4- Evaluation of the security of the protocol
SECONDARY JUDGMENT CRITERIA	
 
1. Descriptive statistics of the verbal scale score
 
2. Descriptive statistics of pain scores recorded during pain assessment using VAS for IVT with conventional topical anesthesia
 
3. Descriptive statistics of the psychological state of the study population. Comparison of the scores obtained between the 2 assessments
 
4. Description of possible side effects
 

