#### IV. - ORGANIZATION OF THE STUDY:

##### A. - SYNTHETIC DESCRIPTION OF THE STUDY SCHEME

[figure not shown]
SYNTHETIC DESCRIPTION	
Monocentric study
 
1. Initial evaluation of the pain felt by patients during an intravitreal injection (IVT) as well as their psychological state before the intervention
 
The basis for this evaluation is a questionnaire completed by the participants before and after the injection.
 
It is composed :
 
 
- A psychological assessment (the HAD Anxiety Scale (Hospital Anxiety and Depression Scale - Authors: AS Zigmond and RP Snaith - French translation JL Lépine) completed by the patient before the IVT
 
- 2 measures for pain assessment using VAS:           
 
o One to assess the pain felt when placing the blepharostat
 
o The other to assess the pain felt when inserting the needle: answer given just after the IVT session.
 
 
 

------------------------------	---

	
2. Selection of patients who felt the most pain (EVA <math>\geq 4/10</math>) and proposal to pass with the protocol: a drop of Tetracaine® or Oxybuprocaine® and a drop of lidocaine gel. Evaluation of pain and relief of patients during IVT with so-called "enhanced" topical anesthesia.
 
The basis for this evaluation also consists of a questionnaire completed by the participants before and after the injection.
 
It is composed :
 
 
- A psychological assessment (HAD Anxiety Scale (Hospital Anxiety and Depression Scale - Authors: AS Zigmond and RP Snaith) completed by the patient before IVT
 
- Of 2 measures for the evaluation of pain using VAS: one to evaluate the pain felt when inserting the blepharostat and the other to evaluate the pain felt when inserting the needle: response performed immediately after the IVT session.
 
- An assessment of pain relief: Simple verbal scale (1 for placing the blepharostat and the other for inserting the needle)
 
 
The answers to the questionnaires will be collected by one of the nurses (TEC or ARC) and the ARC orthoptists and the anonymized data will be sent to the biostatistician of the clinical research department for analysis.

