## B- METHODOLOGY OF QUESTIONNAIRES / INTERVIEWS

AWARDING PROCEDURE	
Questionnaires administered by:
 
 Mail
 
 Internet
 
 Phone
 
 Face to face: during the IVT
 
 Other (explain, list) : .....
 
Questionnaire administered in:
 
 Once
 
 Several times (specify the number of awards): 2
 
Questionnaire type:
 
 Validated
 
 Invalid
 
– if validated, indicate the origin of the validation:
 
For assessment of psychological state and anxiety before the intervention: HAD Anxiety Scale (Hospital Anxiety and Depression Scale - Authors: AS Zigmond and RP Snaith - French translation JL Lépine)
 
For pain assessment: Analogue Visual Scale (EVA): ranging from 1 to 10 cm
 
For assessment of pain relief: Simple verbal scale.
 
– if not validated, justify:
 
Does the research also involve collecting retrospective data:

---------------------------	---

	
 yes
 
 No
 
– if yes, justify:
 
The number of previous IVTs, the pathology requiring the IVT, eye treatments, allergies, history of eye surgery, use of oral analgesics will be collected by the nurses from the patients' medical files.

INTERVIEW	
Methods of realization :
 
 Individual interview
 
 Collective interview
 
Interview carried out in:
 
 Frontface to face during the IVT session
 
 video conference
 
 phone
 
 Other (explain, list) :
 
Interview carried out:
 
 once
 
 several times
 
Number of awards: 2
 
Type of maintenance:
 
 directive
 
 semi-directive
 
 non directive
 
Registration:
 
 No       yes

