DESCRIPTION OF THE DIFFERENT ANESTHETIC EYE DROPS USED DURING IVT	
TETRACAIN 1 PER CENT THEA, eye drops in solution in single-dose container Tetracaine Hydrochloride[25]
 
Eye drops in solution, contains an active substance, Tetracaine®. This substance is a local anesthetic capable of penetrating certain parts of the eye such as the cornea and the conjunctiva.
 
This drug is indicated as a local anesthetic during various surgical procedures or various eye examinations.
 
The side effects listed below are from post-marketing experience with tetracaine. Since these effects were reported spontaneously by a population of indeterminate size, it is not possible to estimate their frequency precisely, which is therefore considered to be indeterminate.
 
 
- Immune system disorders
 
 
Hypersensitivity including erythema, pruritus.
 
 
- Eye conditions
 
 
Keratitis (including ulcerative keratitis), corneal erosion, corneal oedema, eye irritation, eye pain.
 
.
 
OXYBUPROCAINE THEA HYDROCHLORIDE 1.6mg/0.4ml, eye drops in a single-dose container Oxybuprocaine Hydrochloride [26]
 
Ophthalmic local anesthetic

	
Like all medicines, this medicine can cause side effects, although not everyone gets them.
 
 
- A few collapses with bradycardia have been exceptionally reported
 
- Possibility of transient tingling or irritation upon instillation.
 
 
OPHTESIC 20 mg/g. ophthalmic gel in single-dose container  lidocaine hydrochloride[27]
 
OPHTESIC is an anesthetic ophthalmic gel used during ophthalmic procedures.
 
According to the public drug database, the following side effects of lidocaine gel have been described with an unknown frequency:
 
 
- Conjunctival redness, changes in corneal epithelium, eye burning sensation, pitted corneal inflammation, corneal swelling
 

EXPECTED DURATION OF DATA COLLECTION BY INTERVIEW OR QUESTIONNAIRE FOR A PARTICIPANT	
The duration of the interview is estimated at: 5-10 minutes for each questionnaire.

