## RELATED TREATMENTS TO DATA OF PERSONS CONCERNED BY RESEARCHES

Pursuant to Article 5, paragraph 1, point c of the GDPR, the data processed must be adequate, relevant, and limited to what is strictly necessary in relation to the purposes of the processing. In this respect, the data controller undertakes to collect only the data strictly necessary and relevant to the objectives of the research..

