### The answers to the questionnaires

- The answers to questionnaire 1:
  - HAD Anxiety Scale (Hospital Anxiety and Depression Scale - Authors: AS Zigmond and RP Snaith - French translation JL Lépine)
  - Measurement of pain intensity at the time of placement of the **blepharostat**: EVA scale (1 to 10)
  - Measurement of pain intensity at the time of injection: EVA scale (1 to 10)
- The answers to questionnaire number 2(for patients who experienced a significant pain (EVA > 4)

- HAD Anxiety Scale (Hospital Anxiety and Depression Scale - Authors: AS Zigmond and RP Snaith - French translation JL Lépine)
- Measurement of pain intensity at the time of placement of the blepharostat: EVA scale (1 to 10)
- Measurement of pain intensity at the time of injection: EVA scale (1 to 10)
- Measure of pain relief: simple verbal scale (0 to 4)

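### Safety is secondary objective 4, but the available text gives it no data item, time point, recorder or analysis

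*Combined protocol and SAP*

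**What the plan says.** Section III (Objectives and judgment criteria) lists four secondary objectives. The fourth is "Evaluation of the security of the protocol", and its criterion is "Description of possible side effects".

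The places that say what will be collected are these:

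- Section IV.A (Synthetic description of the study scheme) gives each questionnaire a HAD assessment before the injection and two VAS scores. The second adds the relief scale. For the second questionnaire, the timing of the VAS answers is "response performed immediately after the IVT session".
- Section IV.B (Methodology of questionnaires / interviews) names what comes from the medical file: "The number of previous IVTs, the pathology requiring the IVT, eye treatments, allergies, history of eye surgery, use of oral analgesics will be collected".
- Under Data collected categories, the demographic list holds patient number, age and sex, and the Clinical data list has ten items.
- The answers to the questionnaires itemises both forms. The list for questionnaire 2 ends with "Measure of pain relief: simple verbal scale (0 to 4").

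Side effects or symptoms appear in two other places in Section V. The description of the anesthetics says of the gel that "the following side effects of lidocaine gel have been described with an unknown frequency". The exclusion criteria for the second questionnaire screen for redness, burning, corneal pathology and headache present before the injection.

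**The concern.** An objective needs a variable, a time at which it is recorded and someone to record it. Objective 4 has none of these in the text, and the statistical section does not mention safety.

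The gap could not be repaired at analysis. Under Data entry and processing, the biostatistician receives a csv built from the questionnaire answers and has no access to source data. If the file has no side-effect column, nothing can be tabulated. The risk lies in the report: a statement that no side effects were recorded would look like a finding when nobody had been asked.

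The plan itself treats the matter as open, since it gives the gel's side effects as of unknown frequency. It also regards redness, burning and corneal pathology as relevant enough to exclude a patient beforehand, yet does not record them afterwards.

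**Working it through.** The documents state no safety figure, so there is nothing to reproduce. The main check compares the criteria with the data lists.

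**Step 1. Match each secondary criterion to a listed instrument.**

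| Secondary criterion (Section III) | Instrument in the data lists |
|---|---|
| 1. Verbal scale score | Relief scale, questionnaire 2 |
| 2. VAS scores under conventional anesthesia | Two VAS scores, questionnaire 1 |
| 3. Psychological state, compared between assessments | HAD, both questionnaires |
| 4. Side effects | None |

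**Step 2. Look for a post-injection event in every list.**

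- Demographic data: patient number, age, sex. None.
- Clinical data, ten items: prior injections, product, pathology, needle gauge, quadrant, anesthetic, eye treatments, allergies, eye surgery history, oral pain medication. None.
- Medical-file data (Section IV.B): six items, all history or current treatment. None.
- Questionnaire 1: HAD, two VAS scores. None.
- Questionnaire 2: HAD, two VAS scores, relief scale. None.
- Statistical data analysis: pain scores, HAD scores and factors related to pain. No safety analysis.

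The count of side-effect items is zero.

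**Step 3. Check the nearest substitutes.**

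- Allergies are listed as file history, not as a reaction at the session.
- The VAS scores measure pain at blepharostat placement and at needle insertion.
- The symptom check in the exclusion criteria comes before the injection and decides eligibility for questionnaire 2. It is not an outcome.
- The gel's side effects in Section V are product information. Of the five effects named, three are corneal signs, which a patient cannot report reliably without an examination. None is described.

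**Step 4. What could be said if the item were added.**

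Inputs: 40 to 60 patients expected in part 2 and about 300 in part 1 (Section V, number of interviewees). With zero events in n patients, the two-sided exact 95% upper limit is 1 − 0.025^(1/n).

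- n = 40: 1 − 0.025^(1/40) = 0.088, or 8.8%.
- n = 60: 1 − 0.025^(1/60) = 0.060, or 6.0%.
- n = 300 (drops, session 1): 1 − 0.025^(1/300) = 0.012, or 1.2%.

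These limits reflect the number of patients. They do not measure the missing item. They show how a future result of zero should be worded.

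**The case against.** Several points on the other side have weight.

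- **The available text is incomplete.** The questionnaire forms are not reproduced, the study-scheme figure is not shown and some pages were removed. An item could sit there. This cannot be excluded, so the point is limited to what the text describes. Against it, the document itemises the content of both questionnaires, and its table of contents shows no adverse-event section.
- **Complaints could be volunteered.** Section IV.B ticks semi-directive and non-directive interviews, held twice. A patient might mention burning. No listed field would hold the remark, however, and the registration box for the interviews is ticked No. It would therefore be too strong to say that no side effect could ever come to light. What is missing is any planned data.
- **The objective is minor.** It is the fourth secondary objective and only descriptive. Section II cites a favourable regulatory opinion and earlier safety studies of the gel. This bears on priority, and it is right that the primary result is untouched. It does not supply data for an objective the plan chose to state.

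A reader might also draw two stronger inferences that the documents do not support.

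- **That the plan promised a comparison of side effects between the two anesthesia protocols.** Criterion 4 is descriptive. Where a comparison is intended, as in criterion 3, the plan says so.
- **That the data-minimisation commitment bars the collection.** The controller "undertakes to collect only the data strictly necessary and relevant to the objectives of the research". Safety is one of those objectives, so the clause allows a side-effect item.

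**Conclusion.** The point stands as a mismatch between a stated objective and the data lists. In the available text, objective 4 has no item, time point, recorder or analysis, so as written there are no planned observations with which to describe side effects. The practical harm is that silence in the data could be reported as absence of side effects.

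The conclusion assumes that the itemised lists are complete and that the unseen forms add nothing to them. It does not imply that the gel is unsafe, that a comparison was owed, or that the pain analysis is compromised. It is worth correcting because the remedy is small and cannot be applied after the sessions have taken place.

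The upper limits of about 8.8% to 6.0% assume 40 to 60 gel patients with an answer and no events. They bear on how a zero count is interpreted after correction and are not the size of the defect.

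**What to change.** Add one patient-reported side-effect item to the Clinical data or questionnaire lists, completed just after the injection **at both sessions**: yes/no, then redness, burning or irritation, other. Name who records it; the staff who already collect the questionnaires could do so.

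Add to the statistical section:

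- n/N per session with exact 95% confidence intervals. For session 1, give this for all patients and separately for those who go on to part 2, so that the same patients can be set side by side.
- A statement that session 1 is a descriptive within-patient reference for effects of the povidone iodine, the drops and the injection itself. Drops are used at both sessions, so the contrast is gel plus drops against drops alone.
- A statement that corneal signs are not assessed, because no examination is planned.
- A statement that zero events in the gel sessions does not show safety, with the upper limit given beside the count.

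The cost is a slightly longer interview, now estimated at 5 to 10 minutes per questionnaire. The limitation is that only immediate effects noticed by the patient are captured.

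A look-up in the medical file at the next visit is not proposed. It would add follow-up that the plan does not schedule, with injections about every 2 months and the report due in August 2022. It would also conflict with the section on the origin of personal data, which makes the patients the only source and is already at odds with the file extraction in Section IV.B.

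If the item is not added, objective 4 should be withdrawn, or the report should say that side effects were not collected.

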#### IV. - ORGANIZATION OF THE STUDY:

##### A. - SYNTHETIC DESCRIPTION OF THE STUDY SCHEME

[figure not shown]
SYNTHETIC DESCRIPTION	
Monocentric study
 
1. Initial evaluation of the pain felt by patients during an intravitreal injection (IVT) as well as their psychological state before the intervention
 
The basis for this evaluation is a questionnaire completed by the participants before and after the injection.
 
It is composed :
 
 
- A psychological assessment (the HAD Anxiety Scale (Hospital Anxiety and Depression Scale - Authors: AS Zigmond and RP Snaith - French translation JL Lépine) completed by the patient before the IVT
 
- 2 measures for pain assessment using VAS:           
 
o One to assess the pain felt when placing the blepharostat
 
o The other to assess the pain felt when inserting the needle: answer given just after the IVT session.
 
 
 

------------------------------	---

	
2. Selection of patients who felt the most pain (EVA <math>\geq 4/10</math>) and proposal to pass with the protocol: a drop of Tetracaine® or Oxybuprocaine® and a drop of lidocaine gel. Evaluation of pain and relief of patients during IVT with so-called "enhanced" topical anesthesia.
 
The basis for this evaluation also consists of a questionnaire completed by the participants before and after the injection.
 
It is composed :
 
 
- A psychological assessment (HAD Anxiety Scale (Hospital Anxiety and Depression Scale - Authors: AS Zigmond and RP Snaith) completed by the patient before IVT
 
- Of 2 measures for the evaluation of pain using VAS: one to evaluate the pain felt when inserting the blepharostat and the other to evaluate the pain felt when inserting the needle: response performed immediately after the IVT session.
 
- An assessment of pain relief: Simple verbal scale (1 for placing the blepharostat and the other for inserting the needle)
 
 
The answers to the questionnaires will be collected by one of the nurses (TEC or ARC) and the ARC orthoptists and the anonymized data will be sent to the biostatistician of the clinical research department for analysis.

DESCRIPTION OF THE PROCEDURE OF THE IVT	
The injection is performed in the operating room dedicated to IVT at the Jules Verne clinic
 
Anesthesia procedure: reference method:
 
-Instillation of a drop of topical anesthetic: Tetracaine® or Oxybuprocaine®

	
 
- Initial cleansing of the surface of the patient's periocular skin with povidone iodine scrub. Rinse with saline solution and dry with sterile compresses.
 
- Instillation on the conjunctiva of a drop of povidone iodine in a 5% ophthalmic solution. After 2 minutes.
 
- Instillation of 2 drops of anesthetic: Tetracaine® or Oxybuprocaine®
 
 
Anesthesia procedure: with lidocaine gel:
 
 
- Instillation of a drop of topical anesthetic: Tetracaine® or Oxybuprocaine®
 
- Initial cleansing of the surface of the patient's periocular skin with povidone iodine scrub. Rinse with saline solution and dry with sterile compresses.
 
- Instillation on the conjunctiva of a drop of povidone iodine in a 5% ophthalmic solution.
 
- Instillation of lidocaine gel drop
 
 
Procedure common to both anesthesia protocols
 
 
- Preparation of the syringe containing the product to be injected in a sterile manner by the operator as close as possible to the injection
 
- Placement of a sterile drape isolating the patient's eye
 
- Placement of a blepharostat so as to limit the risk of contact between the needle and the free edge of the eyelids or eyelashes.
 
- IVT between 3.5 and 4 mm from the limbus: slow injection of the product
 
- Slow needle withdrawal.
 

--	--

COURSE OF THE STUDY	
The research includes 2 parts:
 

- Evaluation of the prevalence of pain and its intensity during an IVT. Cohort: For 15 days: distribution of the information letter during the consultation to all patients requiring IVT

- Evaluation of the effectiveness of the protocol using a drop of lidocaine gel Cohort: patients experiencing pain requiring management (VAS score <math>\geq 4</math>) and who wish to switch to the enhanced anesthesia protocol

---------------------	--

	
Recruitment of patients will be done on the voluntary participation of patients.
 
The information letter will be submitted for consultation and the evaluation will be scheduled during the next IVT session so that the person has time to reflect before making their decision.
 
Participants may withdraw their consent at any time.

--	--

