INCLUSION CRITERIA 1st QUESTIONNAIRE	
 
- Over 18
 
- Participants having all their capacities of discernment and being able to answer the questionnaires
 
- Patient summoned for an intravitreal injection of an anti-VEGF drug in liquid form (ranibizumab, afibercept, bevacizumab)
 
- Indication for injection: painless retinal pathology (age-related macular degeneration, retinopathy diabetic, macular edema on venous occlusion
 

	
retinal, neovascular membrane on high myopia, or other).
 
-Note information given to the patient and collection of signed non-objection

EXCLUSION CRITERIA 1st QUESTIONNAIRE	
 
- Persons cited in articles L.1121-6 to L.1121-8 of the CSP
 
- Patients not followed at the IOO Jules Verne or at the Hauts Pavés practice.
 
- Eye pain before the procedure
 
- Intravitreal injections performed with oftriamcinolone acetonide
 
- Intravitreal injections performed with a larger gauge needle (Ozurdex® or Iluvien ®)
 
- Intravitreal injections performed using a disinfectant other than povidone iodine
 
- Patients for whom the protocol with lidocaine gel in anesthesia is already used
 
- Any cortisone injection
 
- Any uveitic inflammatory pathology whether immunological or infectious
 
- Anyone under systemic treatment with cortisone or morphine and its derivatives
 

INCLUSION CRITERIA 2nd QUESTIONNAIRE	
 
- Patient with a VAS score during the 1st assessment: VAS <math>\geq</math> 4/10
 
- Patients who have given their consent to switch to the protocol with the addition of lidocaine gel (information letter provided and collection of non-objection)
 

EXCLUSION CRITERIA 2nd QUESTIONNAIRE	
 
- Eye pain before the procedure
 
- patient taking additional or different analgesic treatment compared to the evaluation of the 1st questionnaire
 
- Known allergy to lidocaine or any of the other ingredients of Ophtesic (hypromellose (E464) type 2910, sodium hydroxide (E524), hydrochloric acid (E507))
 
- Presence before IVT of the following symptoms: ocular redness, burning sensation, corneal pathology, headache.
 

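### Does the gel session swap out the later anesthetic drops, leaving the paired t-test unable to answer the stated objective?

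*Combined protocol and SAP*

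**What the plan says.** In section IV.A, the description of the IVT procedure sets out the two anesthesia methods one after the other, then a block of steps common to both. Each method starts with one drop of Tetracaine or Oxybuprocaine and the povidone iodine steps. The reference method then has "Instillation of 2 drops of anesthetic: Tetracaine® or Oxybuprocaine". The gel method has "Instillation of lidocaine gel drop" and lists no further eye drops. The reference list also carries a short timing text, "in a 5% ophthalmic solution. After 2 minutes", which the gel list lacks.

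The main objective in section III describes the test regimen as "a drop of lidocaine gel in addition to a drop of the anesthetic Tetracaine® or Oxybuprocaine", to be judged "compared to the reference anesthesia protocol". The synthetic description in section IV.A gives the same regimen: "a drop of Tetracaine® or Oxybuprocaine® and a drop of lidocaine gel". The second part of the study is labelled "Evaluation of the effectiveness of the protocol using a drop of lidocaine gel".

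The inclusion criteria for the second questionnaire (section V) ask that patients "consent to switch to the protocol with the addition of lidocaine gel". The rationale in section II speaks of drops associated or combined with gel. The primary analysis in section IV.B is a paired t-test of the score under conventional anesthesia against the score under improved anesthesia.

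**The concern.** Someone who reads only the eligibility line would take the second session to be the reference method plus gel. The procedure lists show something else: the two drops after the antiseptic are absent from the gel list and a gel drop is there. If gel replaces drops, the within-patient difference mixes the effect of the gel with the loss of those two drops.

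The stake is interpretation. Suppose the two later drops relieve pain and nothing else differs between sessions. The observed fall in VAS would then understate what gel would add to the full reference method, and a null result would not show that gel adds nothing. Section II makes the distinction more visible. It cites an official opinion that the gel offers no improvement over anesthetic drops, and answers it with the centre's experience of drops given together with gel. A reader could ask which of those two contrasts the study informs.

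**Working it through.** No stated figure needs reproducing here. The check is a count of the listed steps, the algebra of the contrast, and a comparison of the statements.

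**Count (section IV.A, IVT procedure)**

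| Component | Reference | Gel | Gel minus reference |
|---|---|---|---|
| Eye drops before antiseptic | 1 | 1 | 0 |
| Eye drops after antiseptic | 2 | 0 | −2 |
| Gel drops after antiseptic | 0 | 1 | +1 |
| Total eye drops | 1 + 2 = 3 | 1 + 0 = 1 | −2 |

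**Contrast.** Let P(R) be mean pain under the reference list, P(L) under the gel list, and P(R+gel) under a hypothetical full reference method plus gel. With all else equal between sessions,

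P(R) − P(L) = [P(R) − P(R+gel)] − [P(L) − P(R+gel)] = G − D,

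where G is the benefit of adding gel to the full reference method and D is the benefit of the two later drops when gel is present. One paired mean cannot separate G from D. The documents give no value for D, so any figure in centimetres would be invented. The drop count itself is not a measure of effect.

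The identity also assumes that the sessions differ in nothing else. Here patients enter the second part because they scored VAS ≥ 4 at the first session, and the order of sessions is fixed. The observed fall therefore also carries regression to the mean and session effects. G cannot be recovered from it by adding an assumed D. Those effects are a separate matter from the present point.

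**Which quantity does the plan ask for?**

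- Section III, main objective: one drop plus gel, against the whole reference protocol. That is P(R) − P(L).
- Section IV.A, synthetic description: one drop plus one gel drop. Same regimen.
- Section IV.A, course of the study: effectiveness of the protocol that uses gel. Same unit of comparison.
- Section IV.B, main criterion: conventional against improved anesthesia. That is P(R) − P(L).
- Section V, second-questionnaire inclusion: a switch of protocol, with gel added. Addition to the single first drop, as in section III, is a natural reading.
- Section II: associated or combined with gel. Compatible with either reading.

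The four statements that define the comparison agree with one another and with the procedure lists. None asks for G on its own.

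**Timing text.** It is a fragment present in one list only. The document does not show whether it marks a real difference or a break in drafting, so it cannot carry weight either way.

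**The case for a change.** The strongest case for acting is that no sentence states outright that the two later drops are left out. The wording in sections II and V lets a reader assume an add-on, and the data list has a single item for the anesthetic with no specified drop count. If practice departed from the lists, the dataset might not show it. A null finding could then be misread as evidence that gel adds nothing to drops.

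Part of this stands. The contrast is between complete protocols and should be read that way, and a null result would indeed not answer the add-on question. The terms used for the gel regimen and the two-minute text are loose and would need to be reconciled as a matter of drafting.

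The rest does not reach the plan. The omission is visible where it matters, because the two lists stand next to each other and are followed by a block of common steps. The eligibility line makes no claim about effect, and its verb describes a change of protocol. No passage plans a conclusion about gel on top of the full reference method. The lists already fix the number of drops per method, so a count field would serve only to detect departures. It is optional, and the section on data of persons limits collection to what is strictly necessary.

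**Conclusion.** The observation is accurate but calls for no change. As listed, the sessions differ by two fewer eye drops and one more gel drop, so the paired t-test estimates the effect of changing protocol. That is the contrast named in section III, and it is a legitimate question for an evaluation of practice. Following the plan as written answers its stated question, and rewording the eligibility line would leave the analysis, the result and the planned conclusion as they are.

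The residue is clerical: a few terms for the gel regimen, and a timing text found in one list only. Its effect on the result cannot be sized from the documents. The conclusion rests on two assumptions: that the lists describe what is done, which sections III and IV.A support by giving the same one-drop-plus-gel regimen, and that the report words its conclusion at the level of the two protocols, as the objective does. Selection on the first score and fixed session order are outside this point. No position is taken on which procedure is right.
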